9.9. Sample Collection and Handling

If blood samples are collected via an indwelling cannula, an appropriate amount (1 mL) of serosanguineous fluid slightly greater than the dead space volume of the lock will be removed from the cannula and discarded before each blood sample is taken. After blood sample collection, the cannula will be flushed with 0.9% sodium chloride, United States Pharmacopeia (or equivalent)/sodium heparin of 10 U/mL and charged with a volume equal to the dead space volume of the lock. If a mandarin (obturator) is used, blood loss due to discard is not expected. Refer to the Time and Events Schedule for the timing and frequency of all sample collections.

For samples collected from the central laboratory, sample dates and times must be recorded on the laboratory requisition form. Further instructions for the collection, handling, storage, and shipment

of samples are found in the laboratory manual that will be provided. Collection, handling, storage, and shipment of samples must be under the specified, and where applicable, controlled temperature conditions as indicated in the laboratory manual.

Subjects still receiving study treatment after the final CSR analysis will have safety and efficacy assessments performed as per local institution practice (see Attachments 11 and 12).

10. SUBJECT COMPLETION/WITHDRAWAL

10.1. Completion

A subject will be considered to have completed the study if he or she has finished all protocol-specified procedures, has not been lost to follow up, or has not withdrawn consent for study participation before the final OS analysis.

10.2. Discontinuation of Study Treatment

If a subject's study treatment must be discontinued before the end of the treatment regimen, this will not result in automatic withdrawal of the subject from the study. After treatment discontinuation, the subject will move into the Follow-up Phase. The End-of-Treatment Visit and Follow-up visit assessments should continue as specified in the Time and Events Schedule. If study treatment is discontinued for a reason other than disease progression, then disease evaluations will continue to be performed as specified in the Time and Events Schedule.

Subjects who need to discontinue treatment with any one component of study treatment (lenalidomide, dexamethasone, or daratumumab) may continue to receive treatment with the other components of study treatment, as assigned.

A subject's study treatment will be discontinued if:

- The investigator believes that for safety reasons (eg, adverse event) it is in the best interest of the subject to discontinue study treatment
- The subject becomes pregnant or a positive pregnancy test does occur
- The subject (or the subject's legally acceptable representative) withdraws consent for administration of study treatment
- The subject initiates treatment with a prohibited medication
- The subject received concurrent (non-protocol) treatment for multiple myeloma
- The subject experiences unacceptable toxicity, including infusion-related reactions described in Section 6.1.5
- The subject's dose of daratumumab is held for more than 4 weeks in Cycles 1- 6 or for more than 6 weeks in Cycle 7 and beyond (unless Sponsor approves continuation)

• The subject experiences disease progression (please see below). Relapse from CR is not considered as disease progression

A subject who experiences a second primary malignancy that can be treated by surgery may continue to receive the assigned study treatment and the subject should continue to be followed for subsequent progression of multiple myeloma. Subjects who require radiation therapy for treatment of second primary malignancy must have study treatment discontinued unless, upon consultation with the Sponsor and review of data, continuation is agreed upon. Subjects who require systemic treatment of a new malignancy must end study treatment but should continue to be followed for PFS2 and OS.

Before subjects discontinue study treatment due to disease progression, sites will document disease progression (for example by completing a disease progression form or by contacting the IWRS) as soon as possible and within 48 hours. The medical monitor will confirm that treatment should be discontinued. After confirmation from the sponsor, study treatment may be discontinued and the subject entered into Follow-up.

The primary reason for discontinuation of study treatment is to be recorded in the eCRF.

10.3. Withdrawal From the Study

A subject will be withdrawn from the study for any of the following reasons:

- Lost to follow-up
- Withdrawal of consent for study participation
- Death
- The study investigator or Sponsor, for any reason, stops the study or stops the subject's participation in the study

Before a subject is considered lost to follow-up, every reasonable effort must be made by the study site personnel to contact the subject and determine the reason for discontinuation/withdrawal. The measures taken to follow up must be documented.

When a subject withdraws from the study, the reason for withdrawal is to be documented in the eCRF and in the source document. Study treatment assigned to the withdrawn subject may not be assigned to another subject. Subjects who withdraw will not be replaced. If a subject withdraws from the study, assessments outlined in the End-of-Treatment Visit should be obtained.

Withdrawal From the Use of Samples in Future Research

The subject may withdraw consent for use of samples for future research (refer to Section 16.2.5). In such a case, samples will be destroyed after they are no longer needed for the clinical study. Details of the sample retention for research are presented in the main ICF.

11. STATISTICAL METHODS

Statistical analysis will be done by the sponsor or under the authority of the sponsor. A general description of the statistical methods to be used to analyze the efficacy and safety data is outlined below. Specific details will be provided in the Statistical Analysis Plan.

11.1. Subject Information

The primary analysis population will be the intent-to-treat (ITT) population, which will include all randomized subjects. Safety will be evaluated for the population of all treated subjects. The pharmacokinetic analyses will be performed on the pharmacokinetic evaluable population. Continuous variables will be summarized using descriptive statistics such as mean, standard deviation, and range. Categorical variables will be summarized using frequency tables. For time-to-event variables, the Kaplan-Meier method will be used for descriptive summaries.

11.2. Sample Size Determination

The sample size calculation is performed on the basis of the following assumption. Based on the published data, the median PFS for Rd arm is assumed to be approximately 24 months. Assuming that DRd can reduce the risk of the disease progression or death by 25%, ie, assuming the hazard ratio (DRd vs Rd) of 0.75, a total of 390 PFS events is needed to achieve a power of 80% to detect this hazard ratio with a log-rank test (two-sided alpha is 0.05). With a 21-month accrual period and an additional 24-month follow-up, the total sample size needed for the study is approximately 730 (365/arm) subjects. The sample size calculation has taken into consideration an annual dropout rate of 5%.

Long-term survival follow-up was originally planned to continue until 330 deaths had been observed or 7 years after the last subject was randomized. Therefore, this study would achieve approximately 80% power to detect a 27% reduction in the risk of death (hazard ratio 0.73) with a log-rank test (two-sided alpha 0.05). However, after reaching statistical significance at the second interim OS, the long-term survival follow-up will be extended to approximately 390 deaths when the median survival for the DRd group has likely been reached.

11.3. Efficacy Analyses

Response to study treatment and progressive disease will be evaluated by a validated computer algorithm.

Primary Endpoint

For the primary endpoint of PFS, the primary analysis will consist of a stratified log rank test for the comparison of the PFS distribution between the 2 treatment arms. The Kaplan-Meier method will be used to estimate the distribution of overall PFS for each treatment. The treatment effect (hazard ratio) and its two-sided 95% confidence intervals are to be estimated using a stratified Cox regression model with treatment as the sole explanatory variable.

Secondary Endpoints

Other time-to-event efficacy endpoints, including TTP, PFS2, OS, and time to subsequent anti myeloma treatment, will be analyzed using the same method as for PFS. For overall survival, the final analysis will occur after approximately 390 deaths have been observed. Earlier analyses, in which overall survival is analyzed, will be considered as interim analyses. Even though the significance of PFS has already been established at the second interim analysis, testing of OS will continue as planned until a definitive conclusion on OS is reached. The details about testing of OS over time are specified in Section 11.10. The analysis of OS may be confounded by subjects from Arm A receiving daratumumab after disease progression. Exploratory analysis may be performed to adjust for the effect daratumumab exposure may have on OS for the subjects who were randomized to Arm A (Rd).

Comparison between the 2 treatment arms of overall response rates, VGPR or better rate, CR or better rate, and other binary endpoints will be conducted using the stratified Cochran Mantel Haenszel test. The Mantel-Haenszel odds ratio will be provided along with its two-sided 95% confidence interval, and will be provided as the measure of treatment effect. Duration of response will be provided descriptively without formal statistical comparison.

Strong control of familywise Type I error rate will be controlled at a two-sided significance level of 0.05 for the following major secondary endpoints: TTP, CR rate, MRD negativity rate, PFS2 and OS. A sequential hierarchical testing procedure will be used. Details about this hierarchical procedure will be specified in the statistical analysis plan for this study prior to any efficacy analysis.

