4.1. Analysis Specifications

4.1.1. Level of Significance

All statistical hypothesis tests and 95% confidence interval presented will be 2-sided.

The primary hypothesis is to be tested at the 0.05 significance level (overall). The exact significance level at the second interim analysis is to be determined by the observed number of events per the O'Brien-Fleming alpha spending function. Assuming 234 PFS events are observed at the second interim analysis, the alpha to be spent will be 0.0076 (2-sided) for the interim analysis and 0.0476 (2-sided) for the primary PFS analysis (390 PFS events occur). If the observed two-sided p-value is smaller than this significance level as specified above, the superiority of DRd versus Rd with respect to PFS will be established.

If the primary endpoint of PFS is statistically significant, the following secondary endpoints ordered below will be sequentially tested, each with an overall two-sided alpha of 0.05, by utilizing a hierarchical testing approach as proposed by Tang and Geller (1999) that strongly controls Type I error rate:

- 1) CR or better rate
- 2) VGPR or better rate
- 3) MRD negativity rate (10⁻⁵)
- 4) Overall response rate (ORR)
- 5) Overall survival (OS)

These secondary endpoints will be tested at the 2nd IA and the primary PFS analysis. The primary PFS analysis will be skipped if PFS is positive at the 2nd IA. If this is the case, the protocol will be amended to add an analysis for secondary endpoints at a similar timing as the planned primary PFS analysis (note that OS will also be tested at its protocol-specified final analysis). The significance level at the second interim and the primary PFS analyses will be determined by the alpha-spending function specific to endpoints:

- For ORR, VGPR or better rate, CR or better rate, and MRD negativity rate (10⁻⁵), the information fraction is expected to be 80% at the 2nd IA. The O'Brien-Fleming alphaspending function as implemented by the Lan-DeMets method will be used for alphaspending: 0.0244 (two-sided) at the 2nd IA and 0.0428 (two-sided) at the primary PFS analysis.

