- For OS, a modified linear alpha spending function will be used to determine the alpha level at three looks (2nd IA, primary PFS analysis, and final OS analysis). The alpha level will be 0.0001 for the first OS look, and linear spending function will be used to determine the alpha level for the second and last looks. For example, if 59% targeted OS events are observed at the second look, the corresponding alpha level will be 0.0295.

If the null hypothesis for any of these endpoint fails to be rejected at the second interim analysis, then any subsequent endpoint(s) listed above will not be tested until the next analysis time point (e.g., primary PFS analysis), if applicable. If the null hypothesis for an endpoint is rejected at the

second interim analysis, it will remain being rejected and will not be re-tested at any subsequent time points, if any.

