4.3.6.2. Analysis Methods

Similar statistical methods will be applied as described in Section 4.2.2for PFS analysis, including descriptive and comparison of the distribution of overall TTP.

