4.3.7.2. Analysis Methods

Similar statistical methods will be applied as described in Section 4.2.2 for PFS analysis.

4.3.8. sCR Rate

4.3.8.1. **Definition**

sCR rate is defined as the proportion of subjects with a response of sCR based on the computerized algorithm, according to IMWG response criteria, during or after the study treatment

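### Protocol 11.3 claims familywise error control for TTP and PFS2, but the SAP's testing sequence, the only one supplied, gives them no step, boundary or alpha

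*Protocol*

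**What the plan says.** Protocol 11.3 (Secondary Endpoints) claims strong familywise control at two-sided 0.05 "for the following major secondary endpoints: TTP, CR rate, MRD negativity rate, PFS2 and OS". It says a sequential hierarchical procedure will deliver this, and then defers: "Details about this hierarchical procedure will be specified in the statistical analysis plan for this study prior to any efficacy analysis".

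SAP 4.1.1 supplies the procedure. Once PFS is significant, "the following secondary endpoints ordered below will be sequentially tested, each with an overall two-sided alpha of 0.05". The order is CR or better, VGPR or better, MRD negativity at 10^-5, then "4) Overall response rate (ORR"), and OS last. For the four response and MRD rates the levels are "0.0244 (two-sided) at the 2nd IA and 0.0428 (two-sided) at the primary PFS analysis". For OS, "The alpha level will be 0.0001 for the first OS look", with linear spending at the two later looks.

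TTP and PFS2 appear in the SAP only through their analysis methods. SAP 4.3.6.2 sends TTP to the PFS methods, "including descriptive and comparison of the distribution of overall TTP". SAP 4.3.7.2 says of PFS2: "Similar statistical methods will be applied as described in Section 4.2.2 for PFS analysis". The section they point to, SAP 4.2.2, sets out the stratified log-rank test and Cox model and has no multiplicity provision. Protocol 11.10 deals only with looks at PFS and OS.

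**The concern.** The protocol asserts an error-control property for five named endpoints and relies on the SAP to supply it. The SAP supplies it for a different five. TTP and PFS2 are each compared between arms by a log-rank test, so each will yield a p-value, but nothing in the supplied documents ties that p-value to the familywise 0.05.

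What is at stake is which secondary results may be called confirmatory. Someone working from Protocol 11.3 could present a TTP or PFS2 p-value below 0.05 as protected when it is not. The same reader would take VGPR or better and ORR to be unprotected when the SAP does protect them.

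**Working it through.** **1. The SAP's own levels reproduce, so the sequence is taken as sound.** The check uses Lan-DeMets O'Brien-Fleming-type spending with 0.025 per side. The two-sided first-look level is 2 × 2[1 − Φ(z/√t)], with z the 0.9875 normal quantile. The final level is solved from a bivariate normal with correlation √t.

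- PFS, t = 234/390 = 0.60: 0.0076 and 0.0476. The SAP states 0.0076 and 0.0476.
- Response and MRD rates, t = 0.80: 0.0244 and 0.0429. The SAP states 0.0244 and 0.0428, a difference only in the fourth decimal.
- OS, linear spending at 59% of planned deaths: 0.59 × 0.05 = 0.0295, as stated.

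**2. The two lists side by side.**

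| Endpoint | Named in Protocol 11.3 claim | Step in SAP 4.1.1 | Alpha in SAP 4.1.1 (two-sided) |
|---|---|---|---|
| TTP | yes | none | none |
| CR (SAP: CR or better) | yes | 1 | 0.0244, then 0.0428 |
| VGPR or better | no | 2 | 0.0244, then 0.0428 |
| MRD negativity | yes | 3 (at 10^-5) | 0.0244, then 0.0428 |
| ORR | no | 4 | 0.0244, then 0.0428 |
| PFS2 | yes | none | none |
| OS | yes | 5 | 0.0001, then linear |

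Three endpoints are common to both lists (CR, MRD negativity, OS). Two are only in the protocol (TTP, PFS2) and two only in the SAP (VGPR or better, ORR). All secondary alpha goes to the SAP's five.

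**3. Which list do the other sections support?** They are split. Protocol 2.1 and SAP 1.1 open their secondary lists with the five endpoints of Protocol 11.3, in the same order. SAP 1.2 and SAP 4.3 open with the five endpoints of the SAP sequence and put TTP and PFS2 after them.

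**4. What the gap could cost at the design stage.** Assume, before any data, that PFS2 is tested once at two-sided 0.05 outside the sequence, that the sequence spends its full 0.05 over all looks, and that PFS2 and one endpoint in the sequence are truly null.

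- Upper bound: 0.05 + 0.05 = 0.10.
- If independent: 1 − 0.95 × 0.95 = 0.0975.
- Under complete dependence: 0.05.

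The documents do not plan such a stand-alone test, so this shows only what the missing provision would permit. No separate figure is given for TTP: its events (progression, or death due to progression) are a subset of PFS events, and for TTP the matter is mainly one of labelling.

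**The case against.** **It may be no more than an incomplete edit.** The Amendment INT-3 log says the order of secondary objectives and endpoints was changed for consistency with other daratumumab protocols, so the order in Protocol 2.1 need not reflect a testing decision in this trial. The Amendment 5 log says the secondary-endpoint text of 11.3 was revised to match the endpoints due for sequential testing at the second interim analysis. With SAP 1.2 and 4.3, this makes an unfinished alignment at least as plausible as a second, deliberate set of key secondary endpoints. A reader might infer the latter from the matching order in Protocol 2.1 and SAP 1.1, but the documents do not establish it. The objection stands as to cause. It does not repair the current text of 11.3, which still claims control for TTP and PFS2.

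**The details were expressly left to the SAP.** True, and the SAP is explicit. But the protocol deferred how the control works, having itself named the endpoints it covers. The SAP changes that coverage.

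**Versions differ.** The supplied SAP follows Amendment INT-4 and the supplied protocol is Amendment 9. A later SAP could contain a different sequence. This stands, and it limits the finding to the supplied documents.

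**The error-rate figure does not describe this trial.** This also stands. A reader might infer that familywise error here was close to 10%. Protocol 3.1 reports OS superiority at the second interim OS analysis. OS is last in the SAP sequence and cannot be tested until the four steps before it are rejected. If the sequence was followed, that declaration implies CR, VGPR, MRD negativity and ORR had all been rejected already. A scenario that pairs a null PFS2 with a null endpoint from the sequence is therefore not a description of what happened.

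**Conclusion.** The point holds as a mismatch between documents about which endpoints are controlled. In the supplied documents, the familywise control claimed in Protocol 11.3 is not delivered for TTP or PFS2, and the protocol list omits two endpoints that the SAP does control.

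Its reach is limited. The primary PFS conclusion, the OS spending rule, the sample size and the error control of the SAP's five endpoints are untouched, and the SAP sequence is not faulted. The bound of 10% is a pre-data design figure resting on an assumed stand-alone PFS2 test at 0.05. What changes is the status of TTP and PFS2: their p-values are nominal. This should be corrected, because the protocol states a property that the supplied procedure does not provide and the correction is cheap. The conclusion assumes that SAP 4.1.1 is the operative procedure; a later SAP could alter it.

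**What to change.** 1. In Protocol 11.3, replace the list with the SAP 4.1.1 sequence in its order: CR or better, VGPR or better, MRD negativity (10^-5), ORR, OS. Protocol 17.1 requires a formal amendment for this, so make the change in the next one, if there is one.
2. State in SAP 4.3.6.2, SAP 4.3.7.2 and the CSR that TTP and PFS2 p-values are nominal and carry no familywise control.
3. Do not allocate alpha or add steps for TTP or PFS2 now. PFS and OS superiority have been declared, so such an allocation would not be pre-specified.
4. If a later SAP, finalised before the relevant analysis, places TTP and PFS2 in the hierarchy, cite that SAP in 11.3 instead of making changes 1 and 2.

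The cost is about one sentence in each place. No analysis is added and no alpha moves. The downside is that TTP and PFS2 lose the label of controlled endpoints.

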11.4. Pharmacokinetic Analyses

Pharmacokinetic analyses will be performed on the pharmacokinetic-evaluable population, defined as subjects who have received one dose of daratumumab and at least one post-dose sample. All serum concentrations below the lowest quantifiable concentration or missing data will be labeled as such in the concentration data presentation. Concentrations below the lowest quantifiable concentration will be treated as zero in the summary statistics. All subjects and samples excluded from the analysis will be clearly documented in the study report.

Descriptive statistics will be used to summarize daratumumab serum concentrations at each sampling time point and pharmacokinetic parameters of daratumumab such as Cmin and Cmax. If sufficient data are available, then other pharmacokinetic parameters may be calculated, including but not limited to CL and V.

If sufficient data are available, then population pharmacokinetic analysis of serum concentration time data of daratumumab, will be performed using nonlinear mixed-effects modeling. The potential population PK analysis may also include PK data from other studies. If the population pharmacokinetic analysis is conducted, then details will be given in a population pharmacokinetic analysis plan and the results of the analysis will be presented in a separate report.

11.5. Immunogenicity Analyses

The incidence of antibodies to daratumumab will be summarized for all subjects who receive a dose of daratumumab and have appropriate samples for detection of antibodies to daratumumab. The incidence of antibodies to rHuPH20 will be summarized for all subjects who receive a dose of daratumumab SC and have appropriate samples for detection of antibodies.

11.6. Pharmacokinetic/Pharmacodynamic Analyses

If sufficient data are available, then population pharmacokinetic analysis serum concentrations of serum concentration-time data of daratumumab will be performed using nonlinear mixed-effects modeling. If the population pharmacokinetic analysis is conducted, then details will be given in a population pharmacokinetic analysis plan and results of the analysis will be presented in a separate report.

